7.3.1 Collection of Human Biological Specimens. N/A

7.3.1.1 Laboratory evaluations and special precautions. N/A

7.3.1.2 Specimen storage. N/A

7.3.2 Data Collection. Self-report measures (at baseline on paper forms) will be collected at the end of 1 and 6 months. Healthcare utilization will be collected at the end of 12 months.

Self-Report Measures:

Oswestry Disability Index (OSW): The Oswestry Disability Questionnaire, originally described by Fairbank et al⁵⁴ as a condition-specific measure of functional status for patients with LBP. The OSW is a 10-item scale with higher numbers indicating greater disability. We will use the modified version that replaces the sex life item with an employment/ homemaking item due to poor compliance with the former.^{55,56} The OSW is widely used in research on non-operative management of patients with LBP.⁵⁷ Our previous research has found the modified OSW to be used in this study to have high levels of test-retest reliability among stable patients (ICC = 0.90), good construct validity, and responsiveness to change for patients with acute LBP, with a minimum clinically important difference of 6 points for patients with acute LBP receiving physical therapy.⁵⁵ It is a form often used as standard of care in physical therapy clinics.

Neck Disability Index(NDI):

The NDI was created to measure pain related disability associated with activities of daily living in people with neck pain.⁷⁶ The NDI contains ten focused sections. Seven items focus on activities of daily living. These sections include statements related to personal care, lifting, recreational activities, work, driving, and sleeping. Two items focus on the patient's pain. There is one section that evaluates pain directly. The NDI is easy to complete and score. Each item is scored on a 6-point scale and can reach a maximum score of 5; therefore, the maximum score is 50. Higher scores indicating higher levels of disability. Content, construct validity and reliability of the NDI has been previously shown in patients with neck pain.^{76,77} The MCID has been established as a change of 13% (or 6.5 points).⁷⁸

The Opioid Risk Tool: The Opioid Risk Tool is a validated tool to assess the risk of narcotic abuse in patients with chronic pain. It stratifies risk based on age, gender, history of abuse, and psychological disease. A score of 3 or lower indicates low risk for future opioid abuse, a score of 4 to 7 indicates moderate risk for opioid abuse, and a score of 8 or higher indicates a high risk for opioid abuse.⁵⁸ This tool, based on the way that the questions are asked, cannot imply whether the subject currently has a substance abuse issue or a history of one. Therefore, utilizing it as an outcome measure does not alter the current course of treatment from the neurosurgery staff. However, because the Army values the ability for service members to seek care for substance abuse, all subjects will be reminded that the army does have help for substance abuse with the Fort Sam Houston Alcohol and Drug Control Officer (ADCO): [contact] or Military OneSource at [name].

Numeric Pain Rating Scale (NPRS): A 0-10 numeric pain rating scale ('0' indicating no pain, and '10' worst imaginable pain) will be used to assess LBP intensity. Numeric pain scales are known to have excellent test-retest reliability.⁵⁶ Our previous research has found the NPRS to be responsive to change, with a minimum clinically important difference of two points among patients with acute LBP receiving physical therapy.⁹ It is a standard of care measurement taken in physical therapy clinics.

Pain Catastrophizing Scale (PCS): The PCS is a 13-item patient-report scale developed to measure the extent to which people catastrophize in response to pain.⁶⁰ Each item is scored from 0 ('not at all') to 4 ('all the time'). The PCS is reported as a total score, with higher scores indicating greater catastrophizing, and is composed of three sub-scales: Rumination (four items; e.g. 'When I am in pain, I keep thinking about how badly I want the pain to stop'), Magnification (three items; e.g. 'When I am in pain, I become afraid that the pain will get worse'), and Helplessness (six items; e.g. 'When I am in pain, I feel I can't go on') The PCS has been shown to have high levels of internal consistency and construct validity.⁶¹ Pain catastrophizing has also

been found to play a role in the transition from acute to chronic LBP.⁶¹ It is a form often used as standard of care in physical therapy clinics.

Pittsburg Sleep Quality Index (PSQI) The Pittsburg Sleep Quality Index (PSQI) is a self-rated questionnaire which assesses sleep quality and disturbances. Clinical properties provide utility in both psychiatric clinical practices and research activities. Seven “component” scores including: subjective sleep quality, sleep latency, sleep duration, habitual sleep efficiency, sleep disturbances, use of sleep medication, and daytime dysfunction are generated from 19 individual items.⁶³ Sleep quality may have a significant role in affecting outcomes of patients with low back pain as several studies have shown correlation between chronic back pain and quality of sleep.^{70, 71}

Fear Avoidance Belief Questionnaire (FABQ): The⁷² will be used to measure patients’ beliefs about how physical activity and work may affect their pain and perceived risk for re-injury. The FABQ contains two subscales; a 7-item work subscale (FABQW), and 4-item physical activity subscale (FABQPA). Test-retest reliability of the FABQ subscales is high,^{72,73} and validity is supported by associations with disability and work loss in patients with acute and chronic LBP.^{74,75} Heightened fear-avoidance beliefs have been shown to be a risk factor for the development of chronic LBP following an acute episode.^{62,76} Other research suggests it may be appropriate for other body regions, specifically evaluating its use in lower extremity injuries within a physical therapy setting.⁷⁷

Healthcare Utilization

Finally, healthcare utilization data will be collected from the MHS Data Repository (MDR) database and will be confirmed via AHLTA. Healthcare utilization data will be used to determine any opioid medication use along with any subsequent medical utilization related to low back or neck pain. In order to collect this information a DUA will be completed between the researcher team and Patient Administration Systems and Biostatistics Activity (PASBA) and the Tricare Management Agency (TMA). Both of these agencies require a signed completed IRB protocol prior to submitting the DUA. However, this should not impact the timing of this study; as the data pull will be completed no sooner than December 2015. This will provide more than enough time to complete the DUA with both agencies and submit the signed DUA to the BAMC IRB prior to performing this analysis. Details for the determining healthcare utilization are outlined below:

The goal of the MDR database will be to determine the medication utilization for each of these subjects, as well as any other healthcare related to low back pain sought in the 12-month period after treatment in this study. This data (type, location, number of clinic visits, types of specialty clinic visits, imaging, and associated medication) will allow us to determine the extent of low back pain related healthcare utilization for each subject.

- Recording of Extracted Data with Identifiers:

The data will be provided in a de-identified manner from PASBA. As they have done before with members of our team on prior project, they extract all the required data along with name, age and social security number in order to identify the correct subjects that were in our study. They will then assign a pseudo identification number and match that with the list of our subject identification numbers that we provide. Therefore, the final working set they provide us for analysis will not have any identifying PHI/PII associated with it. If additional follow-up is needed to clarify a healthcare utilization event in AHLTA, the research team can check the master subject record (stored on an encrypted government computer) in order to link the subject ID to SSN. Therefore, prior to analysis occurring, the identifiers will be eliminated. Confidentiality of protected health information will be maintained by the research staff at all times, however it should be minimal at this time. The final working database to be used in the data analysis will not include PHI information.

- Location of Extracted and Recorded Data:

The healthcare utilization data will be primarily extracted from the MDR database and through AHLTA. Even though the data is now de-identified, the extracted data will still be maintained in an encrypted, password protected file kept at the Physical Therapy Clinic, Brooke Army Medical Center.

- Nature of Identifying Data

Timeframes will be requested in reference to the baseline enrollment date rather than the actual date. For example, the date of appointment will be required initially to determine when the healthcare visit associated with the back pain occurred. However, this data will be coded differently in the working spreadsheet. The initial appointment will be recorded in weeks from the baseline date of enrollment. If multiple appointments exist, the range of dates will be recorded in the final spreadsheet (e.g. the patient was seen over a 4 week window) and the exact appointment days will not be included in the master spreadsheet. Analysis of the data will only occur in the de-identified spreadsheet.

- Status of the extracted data after completion of the research study:

The de-identified spreadsheet outlined above will be stored indefinitely on a password-protected computer at the Physical Therapy Clinic, Brooke Army Medical Center.

- Redundancy:

In addition to searching the MDR database, at each follow-up visit we will ask subjects if they have utilized healthcare resources since the last follow-up (4 and 26 weeks), specifically related to their LBP in 4 categories: visits to providers (traditional or complementary/alternative), medications (prescription or over-the-counter), interventions (injections, surgery, etc.), or testing (x-rays, MRI, etc.).

7.3.3. Human Biological Specimens/Tissue/Data Banking.

N/A

Statistical Consideration

7.4

7.4.1 *Sample Size Estimation.* Collection of healthcare utilization will occur in 100% of the subjects as no follow-up is required, and therefore no opportunities to collect data from a follow-up visit will be lost. Therefore the sample size estimation is based on the secondary outcome variable of self-reported pain and function (OSW). Assuming at least 85% of patients complete the OSW at 6 months, enrollment of 60 subjects per group (total sample size 120 subjects) will provide at least 84% power to detect a difference of 12 points (2 X MCID) on the change in OSW to 26 weeks, assuming a standard deviation in the change in OSW of 16 points (treatment effect = 43.8% of one standard deviation). The MCID for both the OSW and NDI has been estimated at 6 points.⁵⁵ Previous work with patients with acute LBP indicate that these estimates of anticipated effect size and standard deviation are realistic,⁷⁸⁻⁸⁰ and would be consistent with detecting an effect that is at least slightly in excess of the threshold for seeing significant change. The NDI and OSW are similar in length and answer-type, and as we are expecting a higher number of lumbar patients, we will use the OSW to power this study.

Estimate Required Sample Size	101
Estimate Participant Drop Out / Withdrawal	19
Total Enrollment Requirement	120

Enrollment at Each Site	
--------------------------------	--

BAMC	120
------	-----

7.4.2 Primary (i.e., primary outcome variables) and secondary endpoints.

Primary Outcome Variable: Spinal pain healthcare utilization during the 1 year after enrollment understanding patients are likely still receiving care for their surgery at 6 months. This will include a comparison of imaging orders and types, specialty referrals, and medication use (pain and narcotics).

The self-reported outcome measures will also be taken at baseline, 1 month, and 6 months.

7.4.3 Data analysis.

All data will be analysed in IBM SPSS 21 (Chicago, IL). Descriptive statistics will be performed to describe the sociodemographic (age, sex, race, etc.) and health characteristics (disability, pain intensity, psychosocial factors, etc.) of the entire sample, and comparisons made between groups. Means and standard deviations will be computed for continuous data and frequency distributions will be analysed for categorical data.

Specific Aim #1 will be evaluated by determining the RR (risk ratio) for opioid medication use during the 1 year following surgery between both groups. Utilization reports will be broken down into the 1st week (expected to be the highest), 1st month, and then from 2 through 1 year. We will also look at all healthcare utilization events between patients associated with lumbar ICD-9 codes (Appendix A) in those randomized to also view the educational video.

Comparison of self-report outcomes between groups at baseline and 6 months will be performed using a linear mixed-effects model, which is flexible in accommodating data assumed to be missing at random (Specific Aim #2). The time points will be baseline, 1 month, and 6 months for the measures collected from the patient (self-report questionnaires). Significance is set at 0.05 and 95% confidence intervals will be reported for all relevant data. Sensitivity analysis will be run adjusting for other demographic and/or prognostic variables (PCS, pain intensity, ESS, etc) that may affect the outcome.

Specific Aim #3 will be determined by comparing the variables between each group and introducing them as covariates into the linear mixed-effects model to see if the adjustment influences the differences between each group.

Point estimates with 95% Confidence Intervals will be reported.

7.7 Confidentiality. The only document that will link the subject to the data indirectly is the master patient list. This document will have the patients name, social security number, and assigned subject ID number. This document will be encrypted, password protected, and kept on a CAC-enabled government computer in the BAMC physical therapy section, where only approved study personnel will have access to it. Each subject that consents to participate in the study, will also fill out a contact form that will have their name, email address, and phone number. These documents will be kept in a binder, locked in a research cabinet in a locked office. The master patient list will be referenced when a research team member needs to contact a subject to coordinate follow-up appointment, and needs to correlate the subject ID number with an actual patient. The master list is also needed for when healthcare utilization data is requested from PASBA. At that time, the encrypted file will be emailed to the analyst assigned to work on this project using a government email address, that is digitally signed and encrypted in order to be HIPAA compliance. In essence it will be an encrypted document, that is also being sent via encrypted email. When PASBA returns the healthcare utilization dataset, they will de-identify the data and it will only have a pseudo-ID assigned by the system, along with the subject ID that we had provided. The analysis of the data will

occur with a de-identified data set. The master patient list will be kept for 3 years after the study has been closed out, and then destroyed. The de-identified data will be kept indefinitely for any potential future secondary analysis.

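### Coding repeat appointments as a first week plus a range loses per-window visit counts and types for patients with three or more visits that cross a window boundary

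*Combined protocol and SAP*

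**What the plan says.** Section 7.3.2, under the bullet on the nature of identifying data, sets out how visit timing is stored:

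- Calendar dates are available at first: "For example, the date of appointment will be required initially to determine when the healthcare visit associated with the back pain occurred".
- They are then recoded: "The initial appointment will be recorded in weeks from the baseline date of enrollment".
- For repeat visits, "If multiple appointments exist, the range of dates will be recorded in the final spreadsheet", illustrated by a patient seen over a four-week span.
- Finer timing is dropped: "the exact appointment days will not be included in the master spreadsheet".
- No other file is used: "Analysis of the data will only occur in the de-identified spreadsheet".

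The same section lists the number and type of clinic visits among the variables to be extracted, but not by time window.

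Section 7.4.3 describes the Aim 1 analysis as "determining the RR (risk ratio) for opioid medication use during the 1 year following surgery between both groups" and continues: "Utilization reports will be broken down into the 1st week (expected to be the highest), 1st month, and then from 2 through 1 year". The unit after the last comma is missing; it is read here as month 2 to month 12. The next sentence adds a look at all utilization events under lumbar codes.

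Section 7.4.2 defines the primary outcome as "Spinal pain healthcare utilization during the 1 year after enrollment", comparing imaging orders and types, specialty referrals and medication use. Section 7.1.4 puts the enrollment visit typically 1-2 days before surgery.

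**The concern.** A report by time window needs each event to be placed in a window. The storage rule keeps only the two ends of a patient's series of appointments, and the plan nowhere says that window variables are computed before the dates are coarsened. Followed literally, the analyst receives a file that cannot supply how many visits, or which kinds, fell in week 1, in month 1 and later.

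The affected pattern is one the plan itself anticipates: section 7.4.2 expects patients still to be receiving surgical care at six months, so ranges running past month 1 should be common. The documents give no distribution of visit numbers, so the share of patients affected is unknown.

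A second problem concerns the clock. The stored weeks and the primary outcome run from enrollment, while Aim 1 runs from surgery. A whole-week code cannot be shifted by a day or two afterwards.

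**Working it through.** The plan states no figure on this point, so the check is which quantities remain determined after the storage rule is applied.

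**Inputs.** First week and range (section 7.3.2); total number of visits (listed in section 7.3.2); windows of week 1, month 1 and later (section 7.4.3). Assumptions: the range is anchored to the first visit, so it gives the week of the last one; month 1 is weeks 1-4; weeks run from enrollment.

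**General result.** Take *k* visits, the first in week *f* and the last in week *f + s*. These two are located; the other *k* − 2 are not. If a window boundary falls between first and last, the number of visits before it can be anything from 1 to *k* − 1.

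- *k* = 2: one possible value, so the count is known.
- *k* = 3: two possible values.
- *k* = 5: four possible values.

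Whether there was any visit before the boundary depends only on *f*, and whether there was any after it only on *f + s*. Both are always known.

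**Example.** Five visits, first in week 1, range 20 weeks: the last is in week 1 + 20 = 21 and three visits are unplaced. The week-1, weeks 1-4 and week-5-onward counts can each be 1, 2, 3 or 4, while any-visit is yes for all three. With a range of 3 weeks, all five visits fall in weeks 1-4 and only the week-1 count is unknown (1 to 4).

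**Enumeration.** All histories of 2 to 5 visits by week over an assumed 16-week horizon, equally weighted, with the total known. Entries are the share of histories in which the quantity is uniquely determined.

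| Visits | Histories | Any visit: week 1, weeks 1-4, week 5 on | Any visit: weeks 2-4 only | Week-1 count | Weeks 1-4 and week-5-on counts |
|---|---|---|---|---|---|
| 2 | 136 | 100% | 100% | 100% | 100% |
| 3 | 816 | 100% | 84.6% | 83.5% | 47.1% |
| 4 | 3,876 | 100% | 79.5% | 79.0% | 36.1% |
| 5 | 15,504 | 100% | 75.2% | 75.0% | 28.5% |

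The 47.1% can be checked by hand. With three visits, the month-1 count is ambiguous when the first is in weeks 1-4 and the last is in week *l* = 5 to 16; the middle visit then has *l − f + 1* possible weeks. Summing over both gives 4 × 126 − 12 × 10 + 48 = 432 ambiguous histories, and (816 − 432)/816 = 384/816 = 47.1%.

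The percentages depend on the horizon and weighting and are illustrative. Which quantities are identifiable does not depend on either.

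**Time origin.** If surgery falls 1-2 days after enrollment, week 1 from enrollment contains 1/7 = 14% to 2/7 = 29% pre-operative time, and the first post-operative week straddles stored weeks 1 and 2.

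**The case against.** A reader might infer that the window comparisons cannot be computed for anyone with repeat visits. That goes too far: any-visit indicators for week 1, cumulative month 1 and the later period follow from the first week and an anchored range, two-visit counts are recoverable, and one-year totals do not depend on dates.

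A reader might also infer that the Aim 1 opioid comparison fails. The documents do not support this. The rule is introduced as an example and speaks only of appointments; the coding of dispensing dates is not stated, and silence does not show that they are collapsed. Weekly self-report after surgery (section 7.3) separately covers opioid use in month 1.

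Nor do the documents support a direction of bias, such as early use overstated and late use understated. That would require visits to be allocated by the first appointment, a step that appears nowhere, and the coding rule is the same in both arms.

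The remaining defenses carry some weight. The window sentence sits within the opioid paragraph, and section 7.4.2 names no windows, so per-window visit counts are not an explicit endpoint. Dates exist at first, and nothing forbids deriving window variables from them. Individual events can be checked in AHLTA.

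The conflict nevertheless remains. The sentence concerns utilization reports, the plan does not say that window variables are derived first, and analysis is confined to the coarsened file. The self-report questions on resource use at 4 and 26 weeks neither isolate week 1 nor reach month 12.

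**Conclusion.** The concern holds in a limited form. Under the stated rule, per-window visit counts and visit types generally cannot be recovered for patients with three or more visits whose range crosses a window boundary. Any-visit indicators and one-year totals remain computable, and the one-year opioid risk ratio is not shown to fail.

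This rests on reading the range as anchored to the first visit and month 1 as cumulative. If the range is only an unanchored duration, the later-period indicator also becomes uncertain. If month 1 means weeks 2-4 only, its any-visit indicator is no longer always known.

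The clock mismatch is real but small: 1-2 days, typically, in both arms. It matters mainly for the week-1 window. The share of patients affected by the range rule cannot be computed from the documents.

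**What to change.** Replace the range rule in section 7.3.2 with one row per event (visit, imaging order, referral, prescription fill), each carrying a relative day instead of a calendar date. Alternatively, state that per-window indicators and counts, by event type, are derived before dates are removed. Either way, state how dispensing dates are coded.

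Use one stated time origin in sections 7.3.2, 7.4.2 and 7.4.3, and supply the missing unit in the last reporting window.

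The cost is a change to the data specification given to PASBA, which already needs the dates to make the extract; nothing new is collected from patients. The downside is a slightly larger file that retains relative days. Section 13.0 places the data request in November 2017. If an extract has already been made under the range rule, events can be re-linked only while the master list exists, which section 7.7 limits to three years after close-out.

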4. MILITARY RELEVANCE

The U.S. Armed Forces are experiencing alarming rates of post-war chronic pain related to musculoskeletal disorders.¹ Pain is reported by 40% of OIF/OEF/OND veterans.² Chronic pain after musculoskeletal injury is the leading cause of medical discharge from service³ and a primary source of disability in the U.S.

Military.^{4,5} The costs of chronic pain related disability to the Department of Defense exceed \$1.5 billion annually.⁶ In 2007, musculoskeletal injuries resulted in approximately 2.4 million medical visits to military treatment facilities and accounted for \$548 million dollars in direct patient care costs.⁷ The cumulative incidence of injuries requiring an outpatient visit in U.S. Army entry-level training is about 25% for men and 55% for women.^{8,9} Physical training and sports-related activities account for up to 90% of all injuries^{8,10} and 80% of these injuries are considered overuse in nature.^{11,12}

Military personnel are especially susceptible to the burden of chronic pain. Higher rates of chronic pain are observed in veterans compared to the general population.¹³ Nearly 1 million veterans are prescribed opioids for musculoskeletal conditions, and over half of these individuals chronically use opioids.^{14,15} Military personnel in combat settings are expected to perform duties in extreme operational environments that require very intense physical demands. The body armor and full combat load can be in excess of 120 pounds, which increases the physical demands even further and leaves military personnel at greater risk for back injury and other musculoskeletal disorders.¹⁶ In a survey by Konitzer et al., U.S. Army soldiers reported an increase in the incidence of back, neck, and upper extremity pain during deployment.¹⁶ Considering the demands of a combat load, the incidence of lower extremity musculoskeletal injury is also common among soldiers, which results in significant lost workdays.¹⁷

The U.S. Military faces a post-war chronic pain epidemic. Chronic pain after musculoskeletal injury is the leading cause of medical discharge and related to a growing rate of opioid addiction.¹⁸⁻²² Traditional medical management has failed to correct this chronic pain epidemic.

5. BACKGROUND AND SIGNIFICANCE.

Historical Perspective:

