- 78. Auffinger BM1, Lall RR, Dahdaleh NS, Wong AP, Measuring surgical outcomes in cervical spondylotic myelopathy patients undergoing anterior cervical discectomy and fusion: assessment of minimum clinically important difference. *PLoS One.* 2013 Jun 24;8(6):e67408.

13.0 TIME REQUIRED TO COMPLETE THE RESEARCH (including data analysis).

With an anticipated surgical lumbar surgery load of approximately 20-25 patients per month and a conservative enrollment rate of 50%, we anticipate 1 year for the enrollment period.

- December 2014 – Protocol submitted to BAMC IRB
- April 2015 – Anticipate IRB approval
- March – April 2015 – Study staff training on study procedures
- May 2015 – Subject recruitment/enrollment begins
- May 2017 – Subject recruitment/enrollment end
- November 2017 – Last subject completes 6-month follow-up
- November 2017 – Healthcare utilization data requested from PASBA
- May 2018 – Data analysis and sub-analysis complete
- August 2018 – Publication submitted to appropriate journal

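### The claim of 100% capture of 12-month utilization is unsupported: the timetable and the withdrawal text conflict with it, and nothing verifies that each patient stayed observable

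*Combined protocol and SAP*

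**What the plan says.** Section 7.4.2 makes the primary outcome "Spinal pain healthcare utilization during the 1 year after enrollment". Section 7.4.3 evaluates Aim 1 by "determining the RR (risk ratio) for opioid medication use during the 1 year following surgery between both groups", with separate reports for the first week, the first month and a later window to one year. Section 7.4.1 asserts "Collection of healthcare utilization will occur in 100% of the subjects as no follow-up is required" and gives this as the reason for sizing the trial on a secondary outcome (OSW) instead.

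Section 13.0 lists "May 2015 – Subject recruitment/enrollment begins", "May 2017 – Subject recruitment/enrollment end" and, for November 2017, "Healthcare utilization data requested from PASBA". Analysis is to be complete in May 2018. Section 7.3.2 and the assessment table in Section 7.3 place utilization collection at 12 months. The April 2018 paragraph in Section 7.1.6 explains that collection was extended from 6 to 12 months after contact with participants had ended.

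On checks, Section 7.3.2 has MDR data confirmed in AHLTA, and adds that "we will ask subjects if they have utilized healthcare resources since the last follow-up (4 and 26 weeks".

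On withdrawal, Section 7.1.6 says that subjects who withdraw take no part in further data collection. Section 10.0 says that withdrawal does not affect the primary outcome.

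**The concern.** Needing no study visit is not the same as being observable. A 12-month outcome taken from a database is complete only if 12 months have passed at extraction, if the patient's care was visible to the database throughout, and if the study may use the data. The documents leave all three open. The dates conflict with the window, continued eligibility is never checked, and the withdrawal text points both ways.

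A patient who is no longer visible looks the same in the extract as one who stopped using opioids and sought no care. The plan gives no rule for telling them apart. The missing-at-random statement in Section 7.4.3 concerns the self-report outcomes only. The later window and the utilization counts are most exposed. Use at any time in the year is less so, because Section 7.4.3 expects use to be highest in the first week.

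**Working it through.** **Inputs.** Enrolment May 2015 (month 0) to May 2017 (month 24) and data request November 2017 (month 30), from Section 13.0; 120 patients, 60 per group, from Section 7.4.1; window of 12 months, from Section 7.4.2. Uniform accrual is my assumption.

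**Step 1: the plan's 100%.** With accrual over A months, extraction at month P and a window of W months, the share with an incomplete window is max(0, A − (P − W)) / A.
- Former 6-month window: (24 − (30 − 6)) / 24 = 0. By calendar, the listed dates do give 100%.
- Current 12-month window: (24 − (30 − 12)) / 24 = 6/24 = 25%. Complete capture is 75%, or 90 of 120.

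The listed dates therefore reproduce 100% for the 6-month plan only. Anyone enrolled after November 2016 falls short of 12 months.

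**Step 2: how much is lost.** The 30 affected patients have between 6 and 12 months of data and lose 3 months each on average. This is 30 × 3 = 90 of 120 × 12 = 1,440 person-months, or 6.3%. Counting whole calendar months (25, from May 2015 to May 2017 inclusive), an extract at the end of November 2017 gives 6/25 = 24% incomplete and one at the start gives 7/25 = 28%.

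**Step 3: when the calendar suffices.**
- April 2018 (month 35): (24 − 23) / 24 = 4.2%, or 5 of 120, still incomplete.
- May 2018 (month 36): 0. This is also the month in which Section 13.0 has the analysis finished.
- If accrual had taken the single year that Section 13.0 also mentions, November 2017 would have been late enough for everyone.

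**Step 4: observability, side by side.**

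| Source | What it establishes | What it leaves open |
|---|---|---|
| MDR extract (7.3.2) | Recorded care and medication | Whether an absence of records means no use or no visibility |
| AHLTA (7.3.2) | Confirms and clarifies recorded events | Not used to establish eligibility |
| Self-report (7.3.2) | Utilization at weeks 4 and 26 | Months 7 to 12 |
| Withdrawal text (7.1.6 and 10.0) | Two opposite statements | Whether data after withdrawal are used |

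No section requests eligibility dates or handles death or departure from the system.

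**Step 5: effect on the risk ratio if unobserved users were coded as non-users.** With loss q in both arms, the observed ratio is p₁(1 − q) / [p₀(1 − q)] = p₁/p₀, which is unchanged. Precision falls. As an illustration, take late use of 33.3% in controls (the one-third at one year cited in Section 5) and an assumed 16.7% with education, 60 per arm, two-sided 0.05, normal approximation with pooled variance under the null:

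| Loss in both arms (assumed) | Risk difference, points | Risk ratio | Power |
|---|---|---|---|
| 0% | 16.7 | 0.50 | 56% |
| 5% | 16.7 × 0.95 = 15.8 | 0.50 | 53% |
| 15% | 16.7 × 0.85 = 14.2 | 0.50 | 47% |
| 25% | 16.7 × 0.75 = 12.5 | 0.50 | 42% |

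**The case against.** The strongest reply is that the November 2017 line is stale. It sits beside the last 6-month follow-up visit and predates the April 2018 amendment, and the operative text in Section 7.3.2 already puts collection at 12 months. This stands. A reader might infer that a truncated extract was used; the documents show only that the sections were not brought into line.

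A reader might also infer that missing months are counted as no opioid use. No section says so. It is a likely default when a risk ratio is built from records with no missing-data rule, and no more than that.

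A third inference is that the risk ratio is biased. If 15% were lost in one arm and 5% in the other, and all leavers were coded as non-users, a true ratio of 1 would appear as 0.85/0.95 = 0.89, or as 0.95/0.85 = 1.12 the other way round. The documents do not support these as the expected size. The split is arbitrary. Randomization balances baseline pain, and small permuted blocks nearly balance calendar truncation, so the video itself would have to change who leaves. The figures also require leavers to have no recorded use at all in the window, although use is expected to peak in week 1.

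Nor is loss through discharge established. Section 4 says "Chronic pain after musculoskeletal injury is the leading cause of medical discharge from service", but this describes the Armed Forces in general. Section 7.1.3 does not require active duty, and no section says that discharge ends MDR capture. It makes departure foreseeable and gives no rate.

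What the reply does not answer is that 100% is asserted without any check, that AHLTA and the early self-report do not establish visibility in months 7 to 12, and that the withdrawal statements conflict.

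**Conclusion.** The 100% claim is unsupported for the 12-month outcome and should be corrected. Followed literally, the Section 13.0 dates would leave about a quarter of patients (24% to 28%, depending on the day in November) with under 12 months of data, and about 6% of person-months unobserved. This rests on uniform accrual over the listed two years. An extract in May 2018 or later removes the calendar problem. Even then, capture is complete only if every patient stayed observable, for which the documents give neither a check nor a rate. The size and direction of any bias are unknown. Equal proportional loss would leave the risk ratio unchanged and reduce precision. The exposure lies mainly in the later window and the utilization counts.

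**What to change.** - Correct Section 13.0 so that the extract comes no earlier than 12 months after the last enrolment or surgery (May 2018 or later on the listed dates), and move the analysis date to match. If an earlier extract exists, re-extract for the truncated patients.
- Reconcile Sections 7.1.6 and 10.0 on data after withdrawal.
- Request each patient's eligibility start and stop dates, and date of death, in the same PASBA pull.
- State in Section 7.4.3 how unobserved time is handled. Keep the risk ratio as the main analysis. Add a sensitivity analysis in patients with 12 full observable months, or a risk estimate that allows for censoring.
- Use observed time as an offset only for the utilization counts. Applied to opioid use, it would turn the stated risk ratio into a rate ratio and assume a roughly constant rate, which does not suit use concentrated early after surgery.
- Replace 100% in Section 7.4.1 with the observed proportion, reported by arm.

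The cost is a later or repeated extract, a few extra data fields, some analysis wording and a somewhat smaller sensitivity set. Re-linkage is feasible, since Section 7.7 keeps the master list for 3 years after closure.
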